Heat therapy may be used to target elevated systolic blood pressure and Stage-1 hypertension, as well as to improve numerous biomarkers of cardiovascular disease risk including arterial stiffness. As vascular and cognitive function are closely related, this led us to hypothesize that heat therapy in the form of hot water immersion *may reduce the risk of ADRD*. Therefore, 30 sessions of heat therapy may improve cognitive function and biomarkers of dementia risk assessed using fMRI. As we are performing high resolution cardiovascular phenotyping of our subjects, we will be able to relate changes in biomarkers of cardiovascular health with cognitive function and fMRI-based biomarkers of brain aging and markers of ADRD pathology in mid-life adults. Collectively, these studies will examine relationships between SBP, large artery stiffness (outcome measures in Protocol 1), and tests of cognitive function/brain health (additional outcome measures from Protocol 2) with heat therapy. Thus, the potential benefits of the study greatly outweigh the risks subjects may experience in Protocol 2.

I. Investigator Qualifications, Roles, and Training

[name] has been performing research on biomarkers of cardiovascular health, autonomic-vascular regulation, and human adaptations to environmental extremes for the last 22 years. He has extensive experience performing translational studies in humans utilizing state-of-the-art research and clinical approaches. He has been a leading researcher on vascular and microvascular function in humans in numerous disease states and in understanding the basic mechanisms of blood pressure and blood flow regulation. He has recently published a clinical trial demonstrating that heat therapy can greatly improve biomarkers of cardiovascular health in young, sedentary but otherwise healthy adults.

[name] has extensive experience with exercise physiology, vascular regulation, and has been conducting human studies using many of the proposed methods for 25 years.

[name] is a cardiologist and will provide assistance with the recruitment and screening of individuals with hypertension, as well as provide advice as needed regarding clinical issues which might arise in the execution of this research.

[name], [name], [name], [name], [name], and [name] are all graduate students working under the direction of [name] and [name]. [name] is a postdoctoral fellow working under [name] and [name].

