**Specific Aim 1:** These studies in mid-life adults will determine if heat therapy can be used to improve cognitive aging and dementia risk, with potentially important clinical implications for the prevention of ADRD. Demonstrating that heat therapy can be used as a novel treatment for essential hypertension is timely and important as there is a clear need for alternatives to exercise training and pharmacological approaches. As HTN is linked to ADRD risk, these studies will allow us to link outcome measures in Protocol 1 (focused on CVD risk) with Protocol 2 (focused on ADRD risk) before and after subjects undergo heat therapy or exercise intervention in Protocol 1. The proposed studies are innovative and include an intention-to-treat randomized clinical trial and detailed high-resolution phenotyping to better understand the improvements in blood pressure regulation following heat therapy. *Overall, this work advances a novel treatment option for those with HTN and in the prevention of CVD and ADRD.*

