**Table 4. Derived variables used in study assessments**

Derived Variable	Aim/Primary or Secondary	Description
Protocol 1		
abp_syst	Aim 1/Primary	Continuous; weighted average 24H ambulatory systolic BP
abp_dyas	Aim 1/Primary	Continuous; weighted average 24H ambulatory diastolic BP
abp_day_syst	Aim 1/Secondary	Continuous; average day ambulatory systolic BP
abp_night_syst	Aim 1/Secondary	Continuous; average night ambulatory systolic BP
abp_day_dyas	Aim 1/Secondary	Continuous; average day ambulatory diastolic BP
abp_night_dyas	Aim 1/Secondary	Continuous; average night ambulatory diastolic BP
sv	Aim 1/Secondary	Continuous; stroke volume is calculated as mean_qc*1000/ mean_qc_hr rounded to 3 decimal places
tpr	Aim 1/Secondary	Continuous; total peripheral resistance is calculated as mean_map/mean_qc rounded to 3 decimal places, where mean_map is mean arterial pressure
sbp_dipper	Aim 1/Secondary	Categorical; non-dipper <10%, dipper ≥10% to <20%, and extreme dipper ≥20% change in systolic BP at night calculated from ambulatory BP day and night averages

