## 9 Efficacy Analyses

For primary analyses for Protocol 1 Aims 1, primary outcomes will be compared between groups (heat therapy vs exercise training) over time (within subject repeated measurements) using two-way repeated measures mixed model including an interaction between intervention group and timepoint with pre-defined contrasts. For Specific Aim 1, to test the hypothesis that heat therapy improves blood pressure (both in clinic and 24H ambulatory) better than dynamic aerobic exercise, the null hypothesis will be that the interaction between group and timepoint is equal to 0. For Aim 2, to determine whether heat therapy will improve biomarkers of arterial health (arterial stiffness & biomarkers of systemic

inflammation and oxidative stress) and compare responses to exercise training, the null hypothesis will be that the interaction between intervention group and timepoint is equal to 0. For Aims 1 and 2 exploratory analyses, ANCOVA will be performed for primary and secondary outcomes, with pretest values entered as a covariate and treatment condition specified as a fixed factor. Demographic and physiological variables (age, sex, BMI) and pre-intervention blood pressure will be added one at a time to the ANCOVAs to test for an interaction on treatment effects. For Aim 3, we will use ANCOVA models to determine the predictive potential of acute post-exercise hypotension response for chronic changes in blood pressure, with pretest values entered as a covariate and systolic and diastolic blood pressure specified as a fixed factor. Analyses will be performed on the Intention to Treat population. Additionally, change from pre- to post-intervention in ambulatory and in clinic systolic and diastolic pressure will be correlated with change from pre- to post first intervention session supine systolic and diastolic blood pressure by Pearson correlation.

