For Protocol 2, where composite score cognitive function and brain biomarkers of ADRD risk outcomes were not collected at the interim timepoint, separate linear regressions will be performed for each outcome and predictor combination, where the post-intervention timepoint of the measure is the outcome, the pre-intervention measure of the outcome will be included as a covariate, and predictors will be intervention group in Aim 1 and 24H ambulatory systolic and diastolic blood pressure and arterial stiffness measures mean perfusion calibration in gray matter or white matter in Aim 2. Diagnostic plots and Cook's D of linear regressions will be assessed for influential outliers. If found and not improved through transformation, Robust regression using Huber weighting will be utilized instead.

Continuous outcomes will be transformed for normalcy prior to analysis. Methods used to check model assumptions will include checking for extreme outliers by visual inspection and Shapiro test and checking for homogeneity of variance by visual inspection and Levene's test. Full model results will be saved in an appendix or csv file, for possible use in planning future studies, meta-analysis and to enable replication of analysis.

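### The Protocol 2 Aim 2 regressions give no timepoint for ambulatory BP and no pre-intervention BP term, so they are a weak, confounded test of whether BP change goes with brain outcomes

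*SAP*

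**What the plan says.** SAP 9 defines the outcome side of the Protocol 2 models fully: the post-intervention value is the outcome, and "the pre-intervention measure of the outcome will be included as a covariate". The predictor side is thinner. The SAP says "separate linear regressions will be performed for each outcome and predictor combination", and lists them thus: "predictors will be intervention group in Aim 1 and 24H ambulatory systolic and diastolic blood pressure and arterial stiffness measures". No visit is named for the BP predictor. No change score or pre-intervention BP covariate appears, and because each regression takes one predictor, no other term supplies it.

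SAP Table 4 defines the systolic variable as "Continuous; weighted average 24H ambulatory systolic BP", with a matching entry for diastolic pressure. That is a level at a visit. Where the SAP means change it says so: for Protocol 1 Aim 3, section 9 speaks of "change from pre- to post-intervention in ambulatory and in clinic systolic and diastolic pressure".

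On purpose, Protocol H (Potential Benefits, Protocol 2) says "we will be able to relate changes in biomarkers of cardiovascular health with cognitive function and fMRI-based biomarkers of brain aging". SAP 4.1 wants Protocol 1 and Protocol 2 measures linked "before and after subjects undergo heat therapy or exercise intervention in Protocol 1".

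**The concern.** If the question is whether a change in BP goes with memory or perfusion, the predictor needs its own baseline in the model, just as the outcome has. Without it, the coefficient for post-intervention BP blends stable differences between people with the change over 8 to 10 weeks, and the stable part usually has the larger variance. The coefficient for pre-intervention BP does not measure the change at all; it can reflect it only through any correlation between baseline and change.

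Two things are at stake. A real link between BP reduction and improvement could easily be missed. And a long-standing association between high BP and poorer memory or perfusion, unrelated to either intervention, could be read as the link between the two protocols, because one imperfectly repeatable pre-intervention score does not remove it completely.

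No other planned analysis covers the question. The correlations over time in SAP 9.1 concern the covariates in SAP Table 5, which do not include BP. The later correlations and principal component analysis do include ambulatory BP, but name neither a timepoint nor a change. The output table for these regressions (Table 5 in the SAP's closing list of tables) refers only to associations with blood pressure and arterial stiffness.

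**Working it through.** The documents give no power or effect figure for these regressions, so there is nothing to reproduce. The following is an illustration.

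**Inputs from the documents**
- N = 40, the Protocol 2 maximum (Protocol C).
- s_c = 4.5 mmHg (SAP 6), taken here as the SD of the change in 24-hour BP. SAP 6 does not identify it as an ambulatory change SD.

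**Assumptions not in the documents**
- Baseline BP SD s_0 = 9 mmHg (range 4.5 to 12).
- Outcome retest correlation τ = 0.7 (range 0.6 to 0.8).
- Partial correlation of 0.45 between BP change and the baseline-adjusted outcome.
- Two-sided 0.05.

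**1. Power, with BP change independent of baseline BP**

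The correlation of post-intervention BP with change is s_c/√(s_0² + s_c²) = 4.5/√(81 + 20.25) = 0.447. The partial correlation that the model sees is 0.45 × 0.447 = 0.201. With 37 residual df the noncentrality is r√df/√(1 − r²) = 1.25.

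| Model | s_0 | Partial r | Noncentrality | Power |
|---|---|---|---|---|
| Post BP only | 4.5 | 0.318 | 2.04 | 51% |
| Post BP only | 9 | 0.201 | 1.25 | 23% |
| Post BP only | 12 | 0.158 | 0.97 | 16% |
| Pre BP only | 9 | 0 | 0 | 5% |
| Post and pre BP (36 df) | any | 0.45 | 3.02 | 84% |

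Simulations agree: 22 to 24% for post BP at SD 9 (51 to 52% at SD 4.5, 16 to 18% at SD 12), and 82 to 84% with both terms.

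**2. Power, with equal BP variance before and after**

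Here change is negatively correlated with baseline. The correlation of post BP with change is s_c/(2s) = 4.5/18 = 0.25, so the partial r is 0.45 × 0.25 = 0.1125, the noncentrality 0.69 and power about 10% (11% by simulation). With pre BP added, r = 0.45√(1 − 0.25²)/√(1 − 0.1125²) = 0.438, the noncentrality is 2.93 and power about 81%. Over SD 8 to 12, simulation gives 8 to 11% for post BP alone and 80 to 83% with both. Pre BP alone rejects in 8 to 13%, with the sign reversed.

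**3. Rejection when BP change has no effect**

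Let BP and the outcome have cross-sectional correlation ρ at both visits. The partial correlation of BP with the post outcome, given the pre outcome, is ρ(1 − τ)/√((1 − τ²)(1 − ρ²)).
- Pre BP, ρ = -0.3, τ = 0.7: -0.09/√(0.51 × 0.91) = -0.132, rejection about 12%.
- Post BP: ρ shrinks to -0.3 × 9/√101.25 = -0.268, partial r -0.117, rejection about 11%.

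Over τ from 0.8 to 0.6, simulation gives 8 to 14% for post BP and 10 to 17% for pre BP. With ρ = 0 the rate is about 5%. Adding pre BP to post BP returns it to about 5%.

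**4. Why intervention group belongs in the model**

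Suppose BP change still has no effect, but heat lowers BP by 4 mmHg more (the smallest difference in SAP 6) and shifts the outcome by another route. The model with pre and post BP but no group term rejects in about 12 to 13% of trials for a shift of 0.5 SD and 18 to 20% for 0.7 SD. Adding group restores about 5% and keeps about 82% power at partial r 0.45.

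**The case against.** The best defence is that the change question is not a formal objective. SAP 4.1 lists only an Aim 1 for Protocol 2, its before-and-after wording does not say change, and the explicit reference to changes sits in the Potential Benefits section. The same paragraph also speaks more generally of relationships between systolic pressure, arterial stiffness and brain health, which levels could serve. The output table promises only associations. SAP 7.5 describes the study as hypothesis-generating, and Protocol 2 is a supplementary subset. All of this stands, and it limits the weight of the point. It does not remove the need to say which BP value enters the model, or to fit a suitable model if the change question is to be answered.

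Four stronger readings are tempting, and the documents do not support them.
- That the SAP has fixed BP level as the predictor. No timepoint is given; level is an inference, though the likely one.
- That the model merely asks whether people with high BP differ. The outcome is adjusted for its own baseline, so the test concerns BP against the baseline-adjusted post value.
- That a level carries no information on change. Post-intervention BP contains the change, and the test is diluted rather than empty.
- That the 8 to 17% is the type I error of the model as written. It becomes misleading only if the coefficient is reported as an effect of BP change, and only if a cross-sectional association exists.

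The figures also depend heavily on assumptions: power with post BP runs from about 8% to 52% over the settings tried.

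**Conclusion.** The point holds as a specification defect worth correcting. The firm finding is textual: the timepoint of the BP predictor is unstated, and there is neither a pre-intervention BP term nor a change score. On the natural reading the planned model is a weak and confounded test of the change question in Protocol H. In the central illustration power is about 23% against 83% with pre-intervention BP added; with equal variances it is about 11% against 80%. The direction is the same under both BP models. The sizes rest on an assumed baseline SD, retest correlation and strength of association, and on reading 4.5 mmHg as the SD of change.

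The same SAP sentence contains a second inconsistency. It gives the arterial stiffness predictors as mean perfusion calibration in gray or white matter. SAP Tables 1 and 3 make perfusion a Protocol 2 primary outcome, while Table 1 names pulse wave velocity as the measure of stiffness. Taken literally, a perfusion outcome would appear on both sides of its own regression.

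**What to change.** In SAP 9, write the Protocol 2 Aim 2 model as: post outcome ~ pre outcome + pre-intervention predictor + post-intervention predictor + intervention group. Replacing the post-intervention predictor by the change gives the same test. State that the post (or change) coefficient is the one tested, and title the output Table 5 as associations with change. If an association with level is what is wanted, name the visit and do not report the result as a change effect.

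In the same edit, reconcile the stiffness predictor with SAP Table 1, so that pulse wave velocity and perfusion are not interchanged, and use the same model form for it.

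The cost is SAP wording and two degrees of freedom (37 to 35 at N = 40), or one where only the predictor's baseline is added. Pre-intervention ambulatory BP and the vascular tests are already part of the Protocol 1 pre-tests, and group assignment is known, so no new data are needed.

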### 4.2 Endpoints

In **Protocol 1**, the primary and secondary outcomes from the original grant were updated after interruption from the COVID-19 pandemic shut-downs led to not being able to collect originally planned Aim 2 outcomes: MSNA; FMD;  $\beta$ -stiffness index; Wall thickness, Dynamic arterial compliance; Reactive hyperemia; and Baroreflex sensitivity. In **Protocol 2**, The primary cognitive outcome is a memory domain composite score calculated as the average of age-corrected list-sorting and age-corrected picture sequence z scores. The primary brain biomarker of ADRD risk outcomes are arterial transit time variables mean perfusion in gray matter and mean

perfusion in white matter. The primary and secondary outcomes are shown by protocol and aim in **Table 1** below.

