**Table 1. Outcomes by Protocol and Aim**

Protocol 1			
Outcomes	Aim 1	Aim 2	Aim 3
Primary	Clinic systolic and diastolic pressures; Ambulatory systolic and diastolic pressures	Pulse Wave Velocity (measure of arterial stiffness)	Acute and chronic pressure reductions
Secondary	Heart rate; Cardiac output; Stroke volume; Total peripheral resistance; Secondary BP outcomes: waking, sleeping, dipper vs. non-dipper	Blood-borne biomarkers	
Protocol 2			
	Cognitive	Brain biomarkers of ADRD risk	
Primary Outcomes	Memory domain composite score*	Arterial transit time: mean perfusion in gray matter, mean perfusion in white matter	

\*average of age-corrected list-sorting and age-corrected picture sequence z-scores

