**HEAT THERAPY VS EXERCISE TRAINING IN HYPERTENSION SAP**

dbp_dipper	Aim 1/Secondary	Categorical; non-dipper <10%, dipper ≥10% to <20%, and extreme dipper ≥20% change in diastolic BP at night calculated from ambulatory BP day and night averages
pwv	Aim 2/Primary	Continuous; average of three pulse wave velocity measurements collected at pre-, interim-, and post-intervention timepoints
il6_lg2	Aim 2/Secondary	Continuous; Biomarker IL-6 with the lower limit of detection (LLD) of 0.031 imputed for <LLD, log2 transformed for normalcy
crp_lg2	Aim 2/Secondary	Continuous; Biomarker CRP with the lower limit of detection (LLD) of 0.031 and upper LD (ULD) of 50 imputed for <LLD and >ULD, log2 transformed for normalcy
et1_lg2	Aim 2/Secondary	Continuous; Biomarker ET-1 with the lower limit of detection (LLD) of 0.031 imputed for <LLD, log2 transformed for normalcy
alb_lg2	Aim 2/Secondary	Continuous; Biomarker urine albumin with the lower limit of detection (LLD) of 0.031 imputed for <LLD, log2 transformed for normalcy
Supine.SBP.low	Aim 3/Primary	Continuous; average of three lowest consecutive supine systolic blood pressure measurements taken every 5 minutes for an hour post-intervention during supine recovery (for Heat Therapy: syst_bp55_ht_s1 to syst_bp110_ht_s1; for Exercise Training: for Heat Therapy: syst_bp55_ex_s1 to syst_bp110_ex_s1)
Supine.DBP.low	Aim 3/Primary	Continuous; average of three lowest consecutive supine systolic blood pressure measurements taken every 5 minutes for an hour post-intervention during supine recovery (for Heat Therapy: syst_bp55_ht_s1 to syst_bp110_ht_s1; for Exercise Training: for Heat Therapy: diast_bp55_ex_s1 to diast_bp110_ex_s1)
Supine.SBP.1.ch	Aim 3/Primary	Change from average pre-session resting SBP to Supine.SBP.low
Supine.DBP.1.ch	Aim 3/Primary	Change from average pre-session resting DBP to Supine.SBP.low
eGFR	Aim 1/Exploratory	eGFR was calculated using the CKD-EPI Creatinine-Cystatin Equation (2021) using the CKDEpi_RF.creat.cys function in the nephron R package and rounded to two decimal places
uacr	Aim 1/Exploratory	Urine albumin creatinine ratio (mg/g) was calculated by dividing urine albumin by urine creatinine/1000 rounded to 2 decimal places
Protocol 2		
cognitive_score	cognitive/Primary	Averaged z-scores (centered & divided by standard deviation) of age-corrected picture sequence score (age_cor_score)

		and age-corrected list-sorting score (list_age_cor_scpre)
--	--	--

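### The Protocol 2 Aim 2 regressions name brain perfusion, itself a primary outcome, as the arterial stiffness predictor, and no Protocol 2 analysis names pulse wave velocity

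*SAP*

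**What the plan says.** SAP section 9 sets out the Protocol 2 models. The post-intervention value of each measure is the outcome, and its own pre-intervention value is a covariate. On the crossing rule it says that "separate linear regressions will be performed for each outcome and predictor combination". The predictor is intervention group in Aim 1. In Aim 2 the predictors are 24-hour ambulatory systolic and diastolic pressure and "arterial stiffness measures mean perfusion calibration in gray matter or white matter in Aim 2".

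Elsewhere the SAP uses these terms differently:

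- **Perfusion is an outcome.** SAP 4.2, Table 1 and Table 3 list gray- and white-matter perfusion (mean_pcalib_gm, mean_pcalib_wm) as Protocol 2 primary outcomes. The third primary outcome is the memory composite.
- **Stiffness is PWV.** Table 1 gives the Protocol 1 Aim 2 primary outcome as "Pulse Wave Velocity (measure of arterial stiffness". Table 4 defines it as the "average of three pulse wave velocity measurements collected at pre-, interim-, and post-intervention timepoints". SAP 9.1 attaches the stiffness label to PWV in its Protocol 1 list.
- **Other stiffness-type measures were lost.** SAP 4.2 says that "interruption from the COVID-19 pandemic shut-downs led to not being able to collect originally planned Aim 2 outcomes"; the list that follows includes the β-stiffness index and dynamic arterial compliance.

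The intended link is stated three times. SAP 4.1 says that "these studies will allow us to link outcome measures in Protocol 1 (focused on CVD risk) with Protocol 2 (focused on ADRD risk". Protocol section H undertakes to relate large artery stiffness, identified there as a Protocol 1 outcome, to cognition and brain health. SAP section 15 plans a Protocol 2 Table 5 of associations with blood pressure and arterial stiffness.

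**The concern.** The clause puts a Protocol 2 outcome in the place where a Protocol 1 stiffness measure is expected. An analyst who follows it as printed would fill the stiffness part of planned Table 5 with perfusion coefficients, and the promised stiffness association would not be estimated. The same crossing rule would also pair each perfusion outcome with itself.

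Two omissions make the clause harder to repair by inference. SAP section 9 does not say whether the Aim 2 predictors are pre-intervention values, post-intervention values or changes. Neither document states a Protocol 2 Aim 2: both give only a Specific Aim 1, which in SAP 4.1 opens "These studies in mid-life adults will determine if heat therapy can be used to improve cognitive aging and dementia risk".

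**Working it through.** The SAP prints no model count, so there is no figure to reproduce. The check has three steps.

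**1. Is PWV named anywhere in the Protocol 2 analyses?**

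- SAP 7.3, text: only a generic reference to the outcomes of both protocols.
- SAP 7.3, Table 5 (covariates): sleep, MMSE, hippocampal and white matter hyperintensity measures; no PWV.
- SAP 9, regressions: blood pressure and perfusion; no PWV.
- SAP 9.1, joint list of Protocol 1 and 2 variables: no PWV. This may be a choice and is not counted as an error.
- SAP 15, planned Table 5: arterial stiffness, with no variable named.

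PWV is therefore not named in any of them.

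**2. How many models does each reading give?** The outcomes are the memory composite, gray-matter perfusion (GM) and white-matter perfusion (WM). SBP and DBP are the 24-hour ambulatory pressures.

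| Reading of the clause | Aim 2 models | Stiffness label | Same-variable models |
|---|---|---|---|
| Literal: SBP, DBP, GM, WM, fully crossed | 3 × 4 = 12 | 3 × 2 = 6 carry perfusion | 2 |
| Perfusion predicts cognition only | 3 × 2 + 1 × 2 = 8 | 2 carry perfusion | 0 |
| A comma or an *and* was dropped: SBP, DBP, unnamed stiffness, GM, WM | 3 × 5 = 15 | 3 have no named measure | 2 |
| PWV named: SBP, DBP, PWV | 3 × 3 = 9 | 3 carry PWV | 0 |

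On the literal reading, the 6 perfusion models are memory on GM, memory on WM, GM on WM, WM on GM, GM on GM and WM on WM.

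**3. What do the two same-variable models estimate?** The model is post = b0 + b1·pre + b2·x. With everything on one scale:

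- x = pre: the columns are 1, pre and pre, so the design has rank 2 of 3 and b2 cannot be estimated.
- x = post: b0 = 0, b1 = 0, b2 = 1 fits exactly, so R² = 1.
- x = post − pre: b0 = 0, b1 = 1, b2 = 1 fits exactly, so R² = 1.

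A least-squares check at n = 40, the Protocol 2 maximum, gave the same results: rank 2 of 3 for the pre predictor, and R² = 1.0 for the other two.

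SAP section 9 also says "Continuous outcomes will be transformed for normalcy prior to analysis". If the outcome is transformed and the predictor is not, the exact identities need not hold. The model would still use a measure to explain itself, so it would remain uninformative about stiffness.

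**The case against.** The strongest reply is that this is a slip in one clause and that the SAP lets a reader recover the meaning. Planned Table 5 separates outcomes from predictors, Table 1 and SAP 9.1 attach stiffness to PWV, and protocol section H calls large artery stiffness a Protocol 1 outcome. That makes PWV the likely intention. It does not settle the matter, because the clause prints a different variable in that position. SAP 9.1 uses the same construction, label followed by variable, to name PWV, so the literal reading is the natural one. If a comma or an *and* was dropped, the stiffness measure is unnamed. If perfusion was meant to predict cognition only, it is still mislabelled. The clause needs correcting on every reading. What stands of the reply is that PWV should be confirmed by the sponsor and not assumed.

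It is also fair that the same-variable models arise only under full crossing. On the cognition-only reading there are none.

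A reader might go further and infer that the identity of the two randomized brain outcomes is unclear, because SAP 4.2, Table 1 and Table 3 describe them as arterial transit time while SAP 9.1 lists mean arrival time separately. The documents do not support that. All three places name perfusion, Table 3 gives the dataset variables, and SAP 9.1 repeats the same variable stem. Arrival time appears only in an exploratory list. The outcomes are identified; only the transit-time descriptor is doubtful.

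**Conclusion.** The point holds. As written, the Protocol 2 Aim 2 rule gives the stiffness label to two primary outcomes and leaves the SAP's stiffness measure out of every Protocol 2 analysis. On the literal reading, 6 of 12 models are mislabelled and 2 of those 6 are degenerate on a common scale. The counts assume three primary outcomes and full crossing of outcomes with predictors. The degeneracy also assumes that outcome, covariate and predictor share a scale.

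The reach is limited. This is a non-randomized association in at most 40 people (protocol section C), in a study that SAP 7.5 treats as hypothesis-generating. The randomized PWV comparison in Protocol 1 and the Aim 1 group comparison in Protocol 2 do not use this predictor. The clause is nevertheless more than a typing error, because following it would leave a promised association unestimated. The transit-time wording is a minor labelling matter.

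**What to change.** 1. In SAP 9, subject to the sponsor's confirmation, name PWV as the stiffness predictor alongside 24-hour ambulatory SBP and DBP. Each model is then the post value of the outcome on its pre value plus one predictor, giving 9 models.
2. State one timepoint (pre, post or change) for all three predictors.
3. If perfusion is also wanted as a predictor, list it under its own name, say which outcomes it predicts, and exclude same-variable pairings.
4. State the Protocol 2 Aim 2 objective in SAP 4.1.
5. In SAP 4.2, Table 1 and Table 3, correct or confirm the transit-time descriptor of the perfusion outcomes.
6. Record the dated change in SAP 13.

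The cost is SAP wording, one named predictor and a short confirmation from the sponsor. Table 4 shows PWV already collected at all three timepoints, so no new measurement is needed.
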